7.2 Telephone Follow-up (All patients)

All patients who have been randomised to the trial will be followed up by telephone every three months (6/9/12mths) after week 12 visit. Questions asked during this follow-up will cover hospital attendance (reason/outcome/medication changes/investigations), any symptoms experienced and whether the patient needs to see the research team for an unscheduled visit. The Month 12 questions can be done by either telephone or face to face as a part of the End of Study Visit.

7.2.1 Telephone questions;

The staff making the telephone query will be blinded to the treatment arm and may be from a different site. At the beginning of the conversation the caller will explain that they do not know which treatment arm they are in and that they should try to avoid any references to the treatment and just try and answer the question directly. Please see the Appendix 1 for the details of the telephone questions.

7.3 1-Year Follow-up (All patients)

1st Intervention will be considered baseline, all patient returning for follow-up 1 year \pm 14days after this date. At this visit, all patients will undergo the following assessments:

- Physical Examination
- Vital signs
- Concomitant medications
- ECG
- 24 hour holter monitor tape
- EQ5D quality of life questionnaire
- Adverse Events
- Study Endpoints
- Atrial Fibrillation Effect on QualiTy of life (AFEQT) patient questionnaire

All data will be recorded on the InForm eCRF.

8 Endpoints

8.1 Primary Endpoint:

1. Time to any hospital episode (Emergency Room or patient request for OPD) related to treatment for atrial arrhythmia.

8.2 Secondary Endpoints:

1. Time to death or stroke from any cause.
2. Any complications caused by the procedure (pericardial effusion, bleeding >2 units, phrenic nerve palsy and other) or the anti-arrhythmic drug (GI disturbance, skin irritation and other).
3. All hospital episodes which result in a change in therapy for atrial arrhythmia

All study endpoints will be reported from the date of 1st intervention.

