5.4 Randomisation Procedures

Eligible patients who have given written, informed consent and who meet all the inclusion criteria and no exclusion criteria will undergo 1:1:1 randomisation to an un-blinded treatment of either AVATAR-protocol AF Ablation, medical anti-arrhythmic therapy or conventional AF ablation. Randomisation will be performed electronically using the InForm electronic data capture system and will be stratified by site.

From the date of randomisation, the 1st Intervention date (ablation or anti-arrhythmic medication change) must occur 28 days ± 7days after this, therefore an ablation procedure date will be identified according to local EP catheter lab availability for each consenting, eligible patient and randomisation of the patient will then be scheduled for 28 days ± 7days from this available date.

The patient may be withdrawn from any AF ablation treatment by the Investigator if any safety concerns arise during the period between randomisation and the ablation which make the patient an unsuitable candidate for the procedure. The patient will then be withdrawn from the study.

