7 ASSESSMENT AND FOLLOW-UP

7.1 Discharge Protocol

Patients from the all therapy arms will enter the Discharge protocol 12 weeks \pm 14days post-1st Intervention providing no ongoing symptoms are presented before this.

Patients will be given the centre's Research Nurse contact details and are able to request an unscheduled visit if they experience recurrent symptoms and need hospital review. A blinded research Nurse or designee will contact the patient by telephone every 3 months to ensure that no endpoints have occurred.

The patient will be advised that the blinded research Nurse or designee making the phone call will not know which treatment they have received and the patient will be given a copy of the questions that they will be asked.

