8.4 Endpoint Adjudication

The endpoint adjudication will be done by an independent Endpoint Adjudication Committee (EAC). The EAC will centrally review and classify suspected outcome events, verifying whether they meet protocol definitions. Any hospital episodes (Emergency Room or outpatient) related to treatment for atrial arrhythmia, Stroke or Death from any cause, Any complications caused by the procedure (pericardial effusion, bleeding >2 units, phrenic nerve palsy and other) or the anti-arrhythmic drug (GI disturbance, skin irritation and other), All hospital episodes which result in a change in therapy for atrial arrhythmia.

Any attendance to hospital or specialist cardiac clinic will require the documentation of a discharge letter or clinic letter for primary endpoint adjudication.

Definitions of study endpoints: see Appendix 2

9 Patient visit schedule

PROCEDURE	VISIT (Month)					
	SCREENING (M-0.5 \pm 14d)	1 ST INTERVENTION (M0 \pm 7d)	WK4 REVIEW (M1 \pm 7d)	WK8 REVIEW (M2 \pm 7d)	WK12 REVIEW (M3 \pm 14d)	EOS (M12 \pm 14d)
Obtain Informed Consent	X					
Eligibility Criteria	X					
Vital Signs	X				X	X
Physical Examination	X				X	X
Medical History Assessment	X				X	X
Concomitant Medications	X				X	X
Fasting Blood Sample	X					
Quality of Life Questionnaire	X					X
Allocate 1 ST Intervention date	X					
Randomisation *	X					
Initiate 1 ST Intervention		X				
Allocate possible ablation 're-do' date ** [†]		X				
Review anti-arrhythmic medication			X	X		
Post-ablation symptoms review ** [†]				X	X	
Enter Discharge Protocol					X	
Electrocardiogram						X
24-Hour Holter monitor tape						X
Echocardiogram	X					
Adverse Events		X	X	X	X	X
Study Endpoints			X	X	X	X
AFEQT patient questionnaire	X					X

* = Randomisation date to be scheduled 28d \pm 7d from allocation of 1ST Intervention date

** = AVATAR-protocol ablation arm patients only

† = Anti-arrhythmic therapy arm patients only

^ = Conventional ablation arm patients

10 Safety Reporting

Information about trial adverse events will be collected from randomisation until the end of the trial

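### Allowing the month-12 endpoint questions to be asked face to face means blinded elicitation of hospital attendances is no longer guaranteed for months 9 to 12

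*Protocol*

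**What the plan says.** Protocol 5.4 states that patients "will undergo 1:1:1 randomisation to an un-blinded treatment". Against that background, Protocol 7.1 sets up a blinded check for endpoints: "A blinded research Nurse or designee will contact the patient by telephone every 3 months to ensure that no endpoints have occurred". Protocol 7.2 gives the timing, saying that all randomised patients "will be followed up by telephone every three months (6/9/12mths) after week 12 visit". The same section then adds: "The Month 12 questions can be done by either telephone or face to face as a part of the End of Study Visit".

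The blinding requirement is in 7.2.1: "The staff making the telephone query will be blinded to the treatment arm and may be from a different site". There the caller also tells the patient that they do not know the treatment arm and asks the patient to avoid mentioning treatment. Nothing equivalent is written for a person who asks the questions at the visit.

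Protocol 7.3 lists what else happens at the one-year visit, including concomitant medications, adverse events and study endpoints.

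On what follows once an event is suspected, Protocol 8.4 says: "The EAC will centrally review and classify suspected outcome events, verifying whether they meet protocol definitions". It also requires documents: "Any attendance to hospital or specialist cardiac clinic will require the documentation of a discharge letter or clinic letter for primary endpoint adjudication". SAP 7.1 counts a hospital episode as a primary endpoint only if it has been adjudicated as one by an independent committee. SAP 7.3 lists telephone follow-up as a variable but does not mention the mode of the month-12 interview.

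**The concern.** The primary endpoint includes outpatient attendances made at the patient's request. Whether such an event enters the dataset depends partly on whether someone asks about it and how. The first question in Appendix 1 asks about any hospital attendance, and its first sub-question asks whether the problem was related to atrial fibrillation. In an open-label trial these questions should be put in the same way in every arm, and the blinded caller is the means the protocol chose for this.

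At month 12 the plan allows a route that its blinding rule does not reach, at a visit whose other items readily reveal the arm. Current anti-arrhythmic drugs and procedural complications both point to the allocation. A questioner who knows the arm may probe more in one arm than another. The protocol also does not say who chooses the mode or on what basis, so nothing ensures that the mix of telephone and face-to-face interviews is the same across arms.

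Adjudication does not replace even elicitation, because the committee sees only the events that are found and referred. The documents also do not say that the committee is blinded to arm.

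**Working it through.** **Textual check**

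1. Protocol 7.1 promises a blinded contact by telephone every 3 months. Protocol 7.2 fixes the contacts at months 6, 9 and 12, so the month-12 contact closes the interval from month 9 to month 12.
2. Protocol 7.2 permits that contact to be face to face.
3. Protocol 7.2.1 attaches blinding to the staff making the telephone query. Neither document requires a face-to-face questioner to be blinded.
4. For months 9 to 12, a blinded questioner is therefore possible but not required.

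**Scale of the interval**

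The plan gives no figure for this point, so the calculation below shows only how many events the interval could hold.

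Inputs from Protocol 11.1 and SAP 5.5: 12-month event proportions of 0.63 (anti-arrhythmic), 0.40 (AVATAR) and 0.20 (conventional), with 100 evaluable patients per arm and 103 events in the primary comparison. The event count reproduces: 100 × (0.63 + 0.40) = 103.

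Assumptions, which are not in the documents: event-free survival follows S(t) = (1 − p)^((t/12)^k), with t in months. The base case is k = 1 (constant hazard), and the range is k = 0.5 to 1.25. The month-12 questions are taken to cover the time since the month-9 contact.

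First events per 100 patients in months 9 to 12 = 100 × [(1 − p)^(0.75^k) − (1 − p)].

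At k = 1:

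- Anti-arrhythmic: 100 × (0.37^0.75 − 0.37) = 10.4, which is 17% of 63.
- AVATAR: 100 × (0.60^0.75 − 0.60) = 8.2, which is 20% of 40.
- Conventional: 100 × (0.80^0.75 − 0.80) = 4.6, which is 23% of 20.

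Primary comparison over the range:

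| k | Anti-arrhythmic | AVATAR | Total | Share of 103 |
|---|---|---|---|---|
| 0.5 | 5.3 | 4.3 | 9.5 | 9% |
| 0.75 | 7.9 | 6.3 | 14.1 | 14% |
| 1 | 10.4 | 8.2 | 18.6 | 18% |
| 1.25 | 13.0 | 10.0 | 23.0 | 22% |

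For AVATAR against conventional ablation, the plan implies 100 × (0.40 + 0.20) = 60 events. At k = 1 the interval holds 8.2 + 4.6 = 12.8 of them (21%; 11% to 26% over the same shapes).

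Failure to enter the discharge protocol at week 12 leads to a primary endpoint dated at the subsequent event (Protocol 7.1.1, SAP 7.1). This suggests that events may come early, which favours the lower part of the range.

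**The case against.** The case for leaving the text alone has real force.

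- **The text is silent, not contrary.** A reader might infer that the month-12 questioner is unblinded, or that the trial abandons blinded ascertainment in its last quarter. The documents do not say so. Face to face is an option, nothing says that the questioner knows the arm, and 7.2 can be read as a specific exception to 7.1. Only the guarantee is lost.
- **Letters and adjudication limit the harm.** Every attendance needs a letter, and classification belongs to an independent committee. Many Appendix 1 items are fixed-choice patient answers. This largely disposes of the worry that site staff would classify events differently by arm. What remains is which attendances are elicited and referred.
- **Many events would be known anyway.** Under Protocol 7.1 patients hold the research nurse's contact details and can request unscheduled visits. The clause matters only for attendances that would otherwise go unreported, and the documents give no basis for estimating their number.
- **The telephone blinding is fragile.** Appendix 1 asks about heart drugs, medication changes, procedures and side effects, so a caller may learn the arm in any case. The contrast between call and visit is a matter of degree.
- **Other routes are not stated to be blinded.** The week-12 discharge decision, unscheduled visits and the study-endpoints item at site visits are examples.

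All five points stand as limits on size. None supplies the missing requirement at month 12, and the committee cannot assess an attendance that is never referred to it.

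**Conclusion.** The concern holds in a limited form. Protocol 7.2 opens a month-12 route that the 7.2.1 blinding rule does not cover, so the blinded three-monthly elicitation described in 7.1 is not assured for months 9 to 12. The exposure is confined to attendances that are not otherwise reported.

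Under the planned proportions and a constant hazard, the interval holds about 18.6 of 103 first events in the primary comparison (18%; 9% to 22% for the assumed shapes). A reader might take this as the share of events at risk of bias, which it is not. It counts all first events expected in the interval under an assumed hazard shape, and so caps the number in play. The affected number would be smaller, because an event must also be otherwise unreported, fall in a patient questioned in person by someone who knows the arm, and be elicited differently as a result. The documents do not allow that number, or the direction of any bias, to be estimated.

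The change is worth making because it is cheap and restores a safeguard the protocol already uses at months 6 and 9.

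**What to change.** In Protocol 7.2, replace the open choice of mode with a requirement that the blinded caller complete the Appendix 1 script by telephone at month 12, shortly before the End of Study Visit. Allow face-to-face questioning only if the patient cannot be reached, by a questioner blinded to arm where one is already available. Record mode and blinding status in the eCRF. Require that every attendance reported on the call or at the visit go to the adjudication committee; this also covers the days between the two contacts.

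The cost is a short text change, two eCRF items and one call per patient by the callers already used at months 6 and 9. The small downside is one more contact near month 12. The change does not make the week-12 discharge decision, unscheduled visits or the endpoint item at site visits blinded, and it should not be described as doing so.

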8.3 Crossover between therapies

Following the week 12 visit, a patient from any group, the Investigator may initiate further drug therapy or schedule a standard ablation procedure for the patient. However, the following are required;

- i) *Ablation Arms (Conventional and AVATAR-AF):* Can start anti-arrhythmic drugs or further redo-ablation if there is ECG/Holter documentation of recurrent AF/AT
- ii) *Drug Therapy Arm:* May receive ablation therapy if failed one anti-arrhythmic at maximum standard dose or two anti-arrhythmic agents at sub-maximal dose or due to side effects.
- iii) *New tachycardia documented that needs treatment (VT/AVNRT/AVRT).* The patient is withdrawn from the study

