In summary, developments in paroxysmal AF ablation have been monitored against the definition of any detected 30seconds of AF, which is not necessarily measure of symptom control. Hospital episodes are an objective and well established endpoint throughout the healthcare system and are more reflective of the patient's expectations. The increasing population burden of AF will need more cost effective approaches to treatment of symptoms. It is not known whether current approaches to antral pulmonary vein ablation still necessitates pulmonary vein mapping, which is a major source of to cost and complexity.

The proposed study is based on the following observations:

- i) AF ablation is well established as the most effective method for preventing recurrence.
- ii) Current methods for AF ablation are costly and complex with only a small minority of the AF population having access to such procedure.
- iii) The Advance Cryoballoon is effective at producing antral PV ablation mapping.

iv) AF ablation has not been compared against anti-arrhythmic agents with the primary goal of controlling symptoms.

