5 PATIENT RECRUITMENT

5.1 Patient Selection Procedures

Research staff will identify potential study patients against inclusion and exclusion criteria, before the Investigator determines their eligibility for participation. The Investigator will discuss the rationale for the study, study procedures, risks and benefits and all other issues mandated by the consent process. The potential participant will be offered an opportunity to participate in the study and written informed consent will be obtained if they agree. Study procedures and assessments will only be performed after written informed consent has been obtained.

At the screening visit, the patients general health will be assessed in a physical examination and recording of vital signs. The patient's medical and medication history will also be recorded.

A fasting blood sample will also be taken to exclude patients with uncontrolled diabetes or $[K^+]$ and serum creatinine outside acceptable safety ranges and the patient will be asked to complete a Quality of Life questionnaire (EQ5D) and an Atrial Fibrillation Effect on QualiTy of life (AFEQT) questionnaire. A blood test result within 6 months is acceptable. Any blood test result taken more than 6 months prior to randomisation will need to be repeated. A copy of the blood results must be filed in the patient notes. Any other routine clinical tests should be performed as per local practice.

Both the AVATAR protocol and conventional ablation procedures will be discussed with the patient and the anti-arrhythmic agent or the change in dose that would be selected as the next line of treatment would be agreed at this stage in preparation for potential anti-arrhythmic arm.

The informed consent process and all study assessments will be documented in the patient's medical notes and study case report forms.

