5.6. Schedule of Time and Events

In the 4 week period (28 days \pm 7days) between Randomisation and 1st Intervention, there will be no change to the patient's arrhythmia treatment: the treatment which the patient has been

randomised to will only occur on the date of 1st Intervention. All three treatment arms will follow the same scheduling protocol regardless of intervention.

1st Intervention will be considered baseline, all patient returning for follow-up 1 year \pm 14 days after this date. At this visit, all patients will undergo the following assessments:

- Physical Examination

- Vital signs

- Concomitant medications

- ECG

[figure not shown]
- 24 hour holter monitor tape

- EQ5D quality of life questionnaire

- Adverse Events

- Study Endpoints

- Atrial Fibrillation Effect on QualiTy of life (AFEQT) patient questionnaire

PROCEDURE	VISIT (Month)					
	SCREENING (M-0.5 \pm 14d)	1 ST INTERVENTION (M0 \pm 7 d)	WK4 REVIEW (M1 \pm 7d)	WK8 REVIEW (M2 \pm 7d)	WK12 REVIEW (M3 \pm 14d)	EOS (M12 \pm 14d)
Obtain Informed Consent	X					
Eligibility Criteria	X					
Vital Signs	X				X	X
Physical Examination	X				X	X
Medical History						
Assessment	X				X	X
Concomitant Medications	X				X	X
Fasting Blood Sample	X					
Quality of Life Questionnaire	X					X
Allocate 1 ST Intervention date	X					
Randomisation *	X					
Initiate 1 ST Intervention		X				
Allocate possible ablation 're-do' date **/†		X				
Review anti-arrhythmic medication †			X	X		
Post-ablation symptoms review **/†				X	X	
Enter Discharge Protocol					X	
Electrocardiogram						X
24-Hour Holter monitor tape						X
Echocardiogram	X					
Adverse Events		X	X	X	X	X
Study Endpoints			X	X	X	X
AFEQT patient questionnaire	X					X

* = Randomisation date to be scheduled 28d \pm 7 d from allocation of 1ST Intervention date

** = AVATAR-protocol ablation arm patients only

† = Anti-arrhythmic therapy arm patients only

^ = Conventional ablation arm patients

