8.4. Safety Variable Analysis

Adverse events will be summarised by treatment and severity. A separate table summarising adverse events and their relationship to study treatment will also be produced.

Serious adverse events will be listed and summarised by site, category and treatment. A separate table summarising serious adverse events and their relationship to study treatment will also be produced.

All safety variables will be summarized in the form of frequency tables for categorical variables or descriptive statistics for continuous variables. Quality-of-Life (QoL) questionnaire results will be summarised by Health State Score. Atrial Fibrillation Effect on QualiTy-of-life (AFEQT) questionnaire results will be summarised by both overall AFEQT score and subscale score derived using the formulae stated within the AFEQT Questionnaire Instruction and Scoring Manual

REFERENCES

If it is deemed appropriate, treatment effect will be assessed via t-test for continuous variables and Chi-square test or Fisher exact test for categorical variables (with the appropriate generalized linear model being used). Models containing one or more of the following covariates may also be assessed if deemed necessary: site, weight, hypertension, number of anti-arrhythmics taken by patient prior to 1st intervention. A p-value of 0.025 or less will be considered significant. Any testing for treatment effect will be carried out between AVATAR-AF Ablation and the Anti-Arrhythmic drug treatment arm in order to investigate the primary objective. The secondary objective will be assessed by testing AVATAR-AF Ablation against the Conventional Ablation arm.

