8.5. Health Economic Analysis

A health economist is to analyse selected data to determine the overall economic benefits of antral AF ablation without electrophysiological confirmation of PV isolation. Details of this analysis will be covered in a separate document, external from the SAP.

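### AFEQT and EQ-5D are taken only at screening and month 12, so the pre-crossover effect goes unmeasured, and the planned analysis leaves out the screening score

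*Protocol*

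**What the plan says.** **Timing.** Protocol 5.1 sets the first assessment: at screening "the patient will be asked to complete a Quality of Life questionnaire (EQ5D) and an Atrial Fibrillation Effect on QualiTy of life (AFEQT) questionnaire". Protocol 7.3 sets the second: "1st Intervention will be considered baseline, all patient returning for follow-up 1 year", and both instruments are listed for that visit. The visit tables in Protocol 9 and SAP 5.6 mark them under screening and end of study and nowhere else. SAP Tables 10.1 and 10.2 have only baseline and month-12 columns.

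**Crossover.** The week-12 review includes vital signs, physical examination, history and medication, but no questionnaire. It is the last scheduled visit before Protocol 8.3 takes effect: "Following the week 12 visit, a patient from any group, the Investigator may initiate further drug therapy or schedule a standard ablation procedure". Patients in the ablation arms then need ECG or Holter evidence of recurrence, and patients in the drug arm need drug failure or side effects.

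**Analysis.** SAP 8.4 summarises the quality-of-life questionnaire by Health State Score and AFEQT by overall and subscale scores. Where thought appropriate, "treatment effect will be assessed via t-test for continuous variables and Chi-square test or Fisher exact test for categorical variables", with a generalised linear model mentioned in the same sentence. The optional covariates are site, weight, hypertension and number of previous anti-arrhythmics. SAP 8.5 adds that "A health economist is to analyse selected data to determine the overall economic benefits", with the details left to a separate document.

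**Status.** Patients are randomised to a treatment strategy followed for one year (Protocol 3, SAP 5.2), and evaluation is by intention to treat (SAP 6). Quality of life is in neither endpoint list. SAP 7.3 places it among the safety and efficacy variables.

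**The concern.** Protocol 1.1 gives as one ground for the study that "AF ablation has not been compared against anti-arrhythmic agents with the primary goal of controlling symptoms". AFEQT is the only scored scale specific to atrial fibrillation in the plan. The primary endpoint counts hospital attendances, including visits that the patient requests, and treatment is unblinded. A symptom-related score taken while most patients are still on their allocated treatment would help to show whether fewer attendances reflect better symptom control.

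As scheduled, the only follow-up score comes after some nine months in which patients may have changed treatment. No rule covers these scores after a switch. The censoring sentence in Protocol 11.2 concerns the primary outcome. The per-protocol set in SAP 6 is defined by receipt of the allocated treatment and does not mention later switching.

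Two further losses follow. Two time points cannot show when in the year a change occurred, which any economic analysis based on EQ-5D would need to know. And a score already collected from each patient at screening is not used to sharpen the month-12 comparison.

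**Working it through.** The documents give no sample size, effect or power for AFEQT or EQ-5D, so there is no figure of the plan to reproduce. Every effect size, correlation and crossover rate below is an assumption.

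**1. Gap between crossover and measurement.** Week 12 is day 84 and month 12 is day 365, so the gap is 365 − 84 = 281 days. With ±14 days at each visit it runs from 253 to 309 days. About nine months is right.

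**2. Dilution at month 12.** Assume a true difference d (in SD units) between the initial treatments, a fraction c of the drug arm crossing over, and crossovers reaching the mean of the other arm. The remaining difference is d(1 − c). With 100 patients per arm (the evaluable number in Protocol 11.1), the standard error is √(2/100) = 0.141. At two-sided alpha 0.025 (SAP 8.4), power is Φ(d(1 − c)/0.141 − 2.241).

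| c | Power, d = 0.5 | Power, d = 0.3 |
|---|---|---|
| 0 | 0.90 | 0.45 |
| 0.20 | 0.72 | 0.29 |
| 0.40 | 0.45 | 0.17 |
| 0.63 | 0.18 | 0.07 |

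The last row borrows the planned drug-arm rate of hospital episodes (0.63, Protocol 11.1) as an illustrative ceiling. It is not a crossover rate.

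**3. Path over the year.** Suppose the difference in utility rises linearly to d by month 3 and then moves linearly to d(1 − c) by month 12, with the screening value placed at time zero.

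- Area with a month-3 value: 0.25 × d/2 + 0.75 × (d + d(1 − c))/2 = d(0.875 − 0.375c).
- Area from the two end points only: 0.5d(1 − c).

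| c | With month 3 | Two points | Ratio |
|---|---|---|---|
| 0 | 0.875d | 0.500d | 57% |
| 0.20 | 0.800d | 0.400d | 50% |
| 0.40 | 0.725d | 0.300d | 41% |
| 0.63 | 0.639d | 0.185d | 29% |

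The shortfall is present even with no crossover, because a straight line misses an early gain. The direction depends on the assumed path: if the difference emerged late in the year, two points would overstate the area.

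**4. Use of the screening score.** Compared with an unadjusted t-test of month-12 scores, a linear model with the screening score multiplies the standard error by √(1 − ρ²), where ρ is the correlation between the two scores.

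- ρ = 0.4: √0.84 = 0.917, a cut of about 8%.
- ρ = 0.6: √0.64 = 0.80, a cut of 20%.

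**5. How clean week 12 would be.** A redo ablation is scheduled at 10 weeks ± 7 days (days 63 to 77) and the review at 12 weeks ± 14 days (days 70 to 98). The nominal interval is 14 days. The windows allow anything from almost none to 98 − 63 = 35 days.

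**The case against.** The strongest reply is that the trial compares strategies. Patients are randomised to a one-year strategy and analysed by intention to treat, so the month-12 comparison is a proper randomised estimate of what was assigned, permitted later treatment included. This stands. A reader might infer that the scores cannot show any effect of the assigned treatments. The documents do not support that: what cannot be separated is the effect had nobody switched.

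Other replies, and what remains of each:

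- **Quality of life is secondary to the plan.** It is in no endpoint list. Protocol 1.1 calls such questionnaires cumbersome and argues for hospital episodes instead, and the matching observation in SAP 5.1 ends on hospital episodes where the protocol has symptoms. This stands and limits the weight of the point.
- **No crossover rate is known.** A reader might take the planned 63% as the share of the drug arm that crosses over. It is a hospital-episode rate, and ablation in the drug arm has its own conditions.
- **No trial QALY is planned.** Neither document specifies one, SAP 8.5 speaks only of selected data, and Table 10.1 reports a 0–100 Health State Score. Any effect on QALYs is therefore an inference. It would also be too strong to say that a two-point schedule erases a QALY difference: that requires the drug arm to catch up completely by month 12.
- **The test is not fixed as a t-test.** SAP 8.4 makes testing optional and allows a model with covariates. What remains is that the screening score is not among them.
- **Symptoms are asked about earlier.** The blinded calls at months 6, 9 and 12 record palpitations, other symptoms and perceived need for change. These answers are useful, but they are not a scored scale, and the first call comes after crossover has opened.
- **Week 12 is not a pure comparison either.** Some ablation patients will have had a redo, and drug-arm patients may have had two treatment reviews. This stands, and the week-12 score must be described accordingly.

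**Conclusion.** The point holds in a limited form. The month-12 scores support a valid comparison of one-year strategies. As a measure of the initial treatments that comparison may be diluted, by an amount that depends on a crossover rate the documents do not give. The effect before crossover and the course of quality of life over the year are not measured. The screening score is collected but absent from the covariates in SAP 8.4.

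Under the assumptions shown, 20% to 40% crossover would lower power for a 0.5 SD difference from 0.90 to between 0.72 and 0.45. This assumes that crossovers reach the other arm's mean; less complete catch-up would dilute less. The gain from baseline adjustment, 8% to 20% of the standard error, needs only a correlation of 0.4 to 0.6 between screening and month 12. The area calculation shows how much a two-point path can miss, but whether it matters for the trial rests on an economic plan outside these documents.

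The primary analysis is untouched and quality of life is not a listed endpoint, so this is an improvement of low to moderate importance.

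**What to change.** 1. **SAP 8.4.** State that month-12 AFEQT and EQ-5D scores are compared between randomised arms with a linear model adjusted for the screening score, in place of the optional t-test. This costs one change of wording and needs no new data.
2. **Protocol 9, SAP 5.6 and SAP Tables 10.1–10.2.** Add AFEQT and EQ-5D to the existing week-12 visit in all arms. Analyse that score by randomised arm, with the same adjusted model, as the pre-crossover comparison, and keep month 12 as the strategy comparison.

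The second change costs two short forms at a visit that patients already attend, one more table column per instrument, and a small protocol amendment, which the Trial Steering Committee must approve (Protocol 14.1). It helps only patients who have not yet reached week 12. Its main weakness should be stated with the results: patients who had a redo at about week 10 will be recently post-procedure, so the week-12 score is not a settled effect. Splitting the month-12 scores by crossover status is not recommended, because it forms subgroups after randomisation and adds little.
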